5.7.3.2 Freedom from MBS at 2 Hours Post-Dose

Freedom from each subject's MBS is assessed using the number of mITT subjects who report that their MBS (reported at migraine onset) is absent at 2 hours post-dose. The symptoms that can be nominated as the MBS (phonophobia, photophobia or nausea) are measured using a binary scale (0=absent, 1=present).

Subjects who reported their MBS before taking IP, or who did not provide an MBS are considered failures in this analysis.

Tabulations will be presented as follows:

- The number and percentage of subjects reporting each of the migraine associated symptoms (phonophobia, photophobia or nausea) as most bothersome, subjects with a missing MBS, and subjects who reported their MBS after taking study medication.
- A cross tabulation of the historical MBS (reported at screening) as rows, and the MBS reported at the onset of the treated migraine as columns. This tabulation only includes subjects with both assessments. P-value from a chi-square test will be reported along with the values and confidence limits for both Asymmetric Lambda and Symmetric Lambda.

The estimand, difference in percentage of MBS free subjects ("risk difference") between treatment groups, is evaluated by computing the common risk difference, using CMH weights (sample size weights), stratified by the use of prophylactic migraine medication (yes or no). The risk difference will be tested at a two-sided alpha level of 0.05. Missing data at 2 hours post-dose will be imputed as failure (NC=F). Also the use of rescue medication prior to providing data at the 2 hour assessment, taking IP prior to reporting the MBS, or failure to report a MBS are events that are imputed as treatment failures. If a stratum (prophylactic medication use: yes or no) has sparse data (less than 5 subjects) then the strata will be pooled.

The results to be presented for the primary analysis of MBS include those described in items (a) through (e) for the primary analysis of pain freedom (Section 5.7.3.1). In this case, the "risk" is now the probability of being MBS free at two-hours post-dose.

The primary analysis of MBS will be repeated for the subgroups described in Section 5.2.6.

Sensitivity analyses will be conducted as follows:

- 1. The primary analysis is repeated, once using the mITT subjects that had a qualifying migraine before the last relevant software fix was applied to the eDiaries (onset on or before 13-Sep-2017), and once for mITT subjects with migraine onset dates after the software fix was applied (onset after 13-Sep-2017).
- 2. The primary analysis is repeated, using the mITT population, with missing data at 2 hours post-dose imputed using Last Observation Carried Forward (LOCF). Baseline Observation Carried forward is permitted.
- 3. The primary analysis is repeated, using only data from complete cases (data present at baseline and 2 hours).
- 4. The primary analysis is executed using the mITT analysis set, and multiple imputation (with 20 imputations; m=20) methods to impute missing data at 2 hours post-dose using the copy from reference approach. The FCS method is used with a generalized logit distribution. Covariates may include use of prophylactic medication (yes or no), sex, migraine intensity at onset (severe or other), migraines per month (< median, ≥ median), date of migraine onset (on or before 13-Sep-2017 or after 13-Sep-2017), and the subject's MBS at time of study migraine onset (nausea, photophobia, or phonophobia).

- 5. A matrix of "what if" analyses, similar to that created for the co-primary endpoint of pain freedom, is created for freedom from the MBS.
- 6. The primary analysis will be repeated, using the mITT population, with the addition of a strata that reflects the subject's self-reported MBS at the time of study migraine onset (nausea, phonophobia, or photophobia).

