3 STUDY ENDPOINTS

3.1 Primary

Pain freedom will be assessed using the number of evaluable subjects that report no pain at 2 hours post-dose. Pain will be measured on a 4 point Likert scale (0=none, 1=mild, 2=moderate, 3=severe).

Freedom from the most bothersome symptom (MBS) will be assessed using the number of evaluable subjects that report the absence of their MBS at 2 hours post-dose. The MBS (nausea, phonophobia or photophobia) will be measured using a binary scale (0=absent, 1=present).

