3.2 Secondary

- **Freedom from Photophobia** will be assessed by tabulating the number of subjects that report the absence of photophobia at 2 hours post-dose in the subset of subjects that reported the presence of photophobia at headache baseline.
 - **Freedom from Phonophobia** will be assessed by tabulating the number of subjects that report the absence of phonophobia at 2 hours post-dose in the subset of subjects that reported the presence of phonophobia at headache baseline.
 - **Pain Relief** (aka “headache response”), at 2 hours post-dose, will be assessed using the number of evaluable subjects that report a pain level of moderate or severe (responses of 2 or 3 on the 4 point Likert scale) at baseline and then report a pain level of none or mild (response of 0 or 1) at two hours post-dose.
 - **Freedom from Nausea** will be assessed by tabulating the number of subjects that report the absence of nausea at 2 hours post-dose in the subset of subjects that reported the presence of nausea at headache baseline.
 - The probability of **requiring rescue medication** will be assessed using the number of subjects that take rescue medication within 24 after administration of study medication (BHV3000 or placebo).
 - **Sustained pain freedom**, from 2 to 24 hours, will be assessed using the number of subjects that do not experience any headache pain through the time period of interest.
-

- **Sustained pain relief**, from 2 to 24 hours will be assessed using the number of subjects that do not use any rescue medications, and do not experience any moderate or severe headache pain through the time period of interest.
- **Sustained pain freedom**, from 2 to 48 hours, will be assessed using the number of subjects that do not experience any headache pain through the time period of interest
- **Sustained pain relief** from 2 to 48 hours, will be assessed using the number of subjects that do not use any rescue medications, and do not experience any moderate or severe headache pain through the time period of interest.
- **Pain relapse** will be assessed using the number of subjects that are pain free at 2 hours post-dose and then have a headache of any severity (response of 1, 2 or 3 on the 4 point scale) within 48 hours after administration of study medication (BHV3000 or placebo).
- The proportion of subjects able to function normally, at 2 hours, will be assessed using the number of subjects that self-report as “normal” on the **functional disability** scale.

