6.3.2 Nausea, Phonophobia and Photophobia

The migraine associated symptoms of photophobia, phonophobia and nausea are measured on a two point scale (present or absent), using the eDiary, at the time points listed in [Table 1](#). If a subject reports the presence of a symptom, the subject is then asked to rate the severity of the symptom on a four point scale (none, mild, moderate or severe). All assessment is done using the eDiary.

The subjects are also asked to identify their most bothersome symptom on the eDiary (nausea, phonophobia or photophobia) at the onset of the migraine to be treated. The most bothersome symptom must be identified before the subject takes study medication.

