2.3.1 Primary Estimands

The estimands corresponding to the co-primary endpoints for this study are shown in Table 1.

The population summary for all primary estimands is the difference in the percentage of subjects with a positive result ('risk difference') between the BHV-3000 and the Placebo treatment groups. This summary is computed using the modified Intent-to-Treat (mITT) population as defined in Section 4.1.

Objective	Pain Freedom at 2 hours post-dose	
Population	mITT	
Variable	Percent of subjects reporting no pain at 2 hours post-dose	
Intercurrent Events	NC=F; RM=F;	
Objective	Freedom from Most Bothersome Symptom (MBS)	
Population	mITT	
Variable	Percent of subjects reporting absence of their MBS at 2 hours post dose	
Intercurrent Events	NC=F; RM=F; Failure to report MBS = F; Study medication taken before reporting MBS=F.	

Table 1:Estimands for the Co-Primary Objectives

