2.3.2 Secondary Estimands

The estimands corresponding to the secondary objectives are shown in Table 2.

The population summary for all secondary estimands is the difference in the percentage of subjects with a positive result ('risk difference') between the BHV-3000 and the Placebo treatment groups.

Photophobia Freedom at 2 hours post-dose	
mITT subjects with photophobia reported as present at migraine onset	
Percent of subjects reporting no photophobia at 2 hours post-dose	
NC=F; RM=F	
Phonophobia Freedom at 2 hours post-dose	
mITT subjects with phonophobia reported as present at migraine onset	
Percent of subjects reporting no phonophobia at 2 hours post-dose	
NC=F; RM=F	
Pain Relief at 2 hours post-dose	
mITT	
Percent of subjects who report mild or no pain at 2 hours post-dose	
NC=F; RM=F	
Nausea Freedom at 2 hours post-dose	
mITT subjects with nausea reported as present at migraine onset	
Percent of subjects reporting no nausea at 2 hours post-dose	
NC=F; RM=F	
Probability of Rescue Medication	
mITT	
Percent of subjects taking rescue medication	
None	
Functional Disability at 2 hours	
mITT	
Percent of subjects with a response of "normal" at 2 hours post-dose	
NC=F; RM=F	
Sustained Pain Freedom (2 to 24 hours; or 2 to 48 hours)	
mITT	
Percent of subjects pain free during the period of interest	
NC1=F; RM=F	
Sustained Pain Relief (2 to 24 hours; or 2 to 48 hours)	
mITT	
Percent of subjects who report no pain, or mild pain, during the period of interest	
NC1=F; RM=F	
Pain Relapse (2 to 48 hours)	
- · · · · · · · · · · · · · · · · · · ·	
mi i i subjects who report bain freedom at 2 nours post-dose	
mITT subjects who report pain freedom at 2 hours post-dose Percent of subjects who report any pain during the period of interest	

Table 2: Estimands for the Secondary Objectives

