2.2 Time to First Report of Absence of Various Symptoms

For each of the following variables, two sets of Kaplan-Meier plots and tables were created:

- Time to First Report of Absence of Most Bothersome Symptom
- Time to First Report of Absence of Nausea
- Time to First Report of Absence of Photophobia
- Time to First Report of Absence of Phonophobia
- Time to First Report of Return to Normal Functioning

The first set of plots and tables was similar to those created for the time to rescue medication (using actual time). For the second set of plots, nominal (planned time point) as opposed to actual time was used for clinical event times. Censoring was measured using actual time as in all previous plots.

For both sets of analyses, the analysis population for MBS and functional disability was the set of mITT subjects. The analysis population for nausea, phonophobia, and photophobia was the subset of mITT subjects that reported the symptom as present at the onset of their study migraine. The y-axis for all plots represents the probability of the occurrence of the event of interest, and therefore are increasing from left to right.

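### The co-primary MBS endpoint does not require the nominated symptom to be recorded as present at onset, so a symptom rated absent before dosing and again at 2 hours scores as a success

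*SAP*

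**What the plan says.** Protocol 3.1 defines the endpoint by "the number of evaluable subjects that report the absence of their MBS at 2 hours post-dose". SAP 2.3.1, Table 1, gives the variable as "Percent of subjects reporting absence of their MBS at 2 hours post dose", and SAP 5.7.3.2 counts "the number of mITT subjects who report that their MBS (reported at migraine onset) is absent at 2 hours post-dose". The events scored as failure in Table 1 are "NC=F; RM=F; Failure to report MBS = F; Study medication taken before reporting MBS=F". A nominated symptom recorded as absent at onset is not among them.

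Protocol 6.3.2 has the subject make two separate entries at onset: each of the three symptoms is rated present or absent, and one is named as most bothersome. It adds: "The most bothersome symptom must be identified before the subject takes study medication". The mITT definition (SAP 4.1) asks for moderate to severe pain at baseline and one post-baseline efficacy data point, but no associated symptom.

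The single-symptom endpoints are treated differently. Protocol 3.2 assesses photophobia freedom "in the subset of subjects that reported the presence of photophobia at headache baseline", and SAP Table 2 sets its population as "mITT subjects with photophobia reported as present at migraine onset". Phonophobia and nausea follow the same rule. SAP Appendix 3 keeps the split: in its section 2.2 the single symptoms are limited to subjects who had them at onset, while "the analysis population for MBS and functional disability was the set of mITT subjects".

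One sentence of SAP 5.7.3.2 calls subjects who reported their MBS before dosing failures. It conflicts with Table 1, with SAP 5.7.2 and with later text of 5.7.3.2, so Table 1 is followed here.

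**The concern.** Freedom from a symptom that was not there before dosing is not evidence of treatment benefit. The same record is also handled in two ways. A subject who names photophobia but rates it absent at onset is left out of the photophobia endpoint, yet is an MBS success if it is absent at 2 hours. Such subjects would tend to succeed in both arms, which raises both reported rates and dilutes the difference on a co-primary endpoint.

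The planned sensitivity analyses do not expose this. The complete-case analysis needs baseline data to be present, not the symptom. Sensitivity analysis 6 stratifies by the named symptom without conditioning on its presence. Sensitivity analysis 2 permits baseline carry-forward, so with no usable later rating up to 2 hours, an absent rating at onset would itself become a success.

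**Working it through.** **Inputs.** From protocol 1.4.2, Phase 2b symptom freedom at 2 hours, 75 mg vs placebo: photophobia 41.9% vs 24.1%, phonophobia 52.3% vs 28.1%, nausea 67.4% vs 51.2%. The documents give no Phase 2b MBS rate, so these serve as proxies. From protocol 9.2 and SAP 5.1: 550 treated subjects per arm and stated power above 95%. The test is two-sided at 0.05 with 1:1 allocation.

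**The plan's own figure.** Power = Φ((d − 1.96 × SE0)/SE1), with pooled SE0 and unpooled SE1. For photophobia, d = 0.178 and the pooled rate is 0.330:

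- SE0 = √(2 × 0.330 × 0.670/550) = 0.02836
- SE1 = √((0.419 × 0.581 + 0.241 × 0.759)/550) = 0.02784
- Power = Φ(4.40), above 99.99%

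Phonophobia also gives above 99.99%, and nausea 99.98%. The stated figure is consistent with all three proxies.

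**Effect of the gap.** Let f be the share of subjects whose nominated MBS was recorded absent at onset, and s the share of those with it absent at 2 hours and scored as success. Both are assumptions, taken as equal in the two arms. If p is the rate among subjects who had the symptom:

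observed rate = (1 − f) × p + f × s, and difference = (1 − f) × 17.8 points.

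With s = 0.90 and the photophobia proxy:

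| f | Rimegepant | Placebo | Difference (points) | Placebo overstated by (points) |
|---|---|---|---|---|
| 0% | 41.9% | 24.1% | 17.8 | 0 |
| 2% | 42.9% | 25.4% | 17.4 | 1.3 |
| 5% | 44.3% | 27.4% | 16.9 | 3.3 |
| 10% | 46.7% | 30.7% | 16.0 | 6.6 |

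For example, at f = 10% on placebo: 0.9 × 24.1 + 0.1 × 90 = 30.7.

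**Three ways to handle these subjects at f = 10%** (z = difference / unpooled SE):

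| Handling | Rates | Difference (points) | n per arm | SE | z |
|---|---|---|---|---|---|
| As written | 46.7% vs 30.7% | 16.0 | 550 | 0.0290 | 5.5 |
| Scored as failure | 37.7% vs 21.7% | 16.0 | 550 | 0.0271 | 5.9 |
| Restricted to symptom present at onset | 41.9% vs 24.1% | 17.8 | 495 | 0.0293 | 6.1 |

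The failure rates are 0.9 × 41.9 and 0.9 × 24.1; the restricted n is 0.9 × 550. Scoring as failure removes the spurious successes and some variance, but the difference remains (1 − f) × 17.8. It also puts both rates below those of subjects who had the symptom, by 4.2 and 2.4 points. Only restriction recovers 17.8.

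**Power.** With s from 0.8 to 1.0, the three proxies and f up to 10%, the lowest power as written is 99.88% (nausea, f = 10%, s = 0.8). With f as high as 20%, the lowest under any of the three handlings is 99.1% (nausea, scored as failure).

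**The case against.** The strongest reply is that the case may never arise. Protocol 4.3.2 and footnote 2 of the assessment schedule ask for the symptom that is most bothersome at the time, which implies one the subject has. The eDiary may offer only symptoms marked present; its specification is not in the documents. This stands as a limit on size: f may be zero. It does not supply an analysis rule. The SAP already provides for missing and late nominations, although the protocol instructs against both, so it does not rely on instructions being followed.

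A reader might infer that a subject with pain but no associated symptom is forced to name one in order to dose, so the problem must occur. The documents do not support that. SAP Table 1, the missing-data subgroups in SAP 5.6 and the tabulation in 5.7.3.2 all allow for subjects with no MBS reported, and these are already failures. Some of the group in question may therefore be covered.

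A reader might also infer that the gap favours rimegepant or endangers the secondary sequence that this endpoint gates. Neither follows. The nomination is made before dosing in a randomised, blinded trial, so under no drug effect both arms behave alike and type I error is not inflated. With equal shares the bias in the difference is toward zero, and power barely moves.

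**Conclusion.** The gap is real on the text: a nominated symptom rated absent at onset and at 2 hours, named before dosing and without rescue, is a co-primary success. For f of 0 to 10%, the placebo rate is overstated by 0 to 6.6 points, and the difference falls from 17.8 to as low as 16.0 points.

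These sizes rest on three assumptions: that f and s are equal across arms, that s is 90%, and that photophobia stands in for MBS. None of these comes from the trial's own MBS data. If rimegepant also kept absent symptoms from appearing, s would differ between arms and the dilution would be smaller.

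The consequence is for the validity and readability of the reported rates. The documents give no ground for a false-positive or power problem. The change is worth making because the SAP already applies the presence rule to each single symptom.

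**What to change.** 1. In SAP 5.7.3.2, add a row by arm to the MBS tabulation for subjects whose nominated MBS was recorded absent at onset. A count of zero settles the matter.
2. Add an analysis of MBS freedom restricted to mITT subjects whose nominated MBS was recorded present at onset, mirroring SAP Table 2 and 5.7.4.1.
3. In sensitivity analysis 2, state that an absent rating at onset is not carried forward as a success.
4. If the full mITT denominator is kept for the primary analysis, these subjects may be scored as failures there. The restricted analysis is still needed, because that scoring does not undo the dilution. A change to the primary rule must be made consistently in SAP Table 1, SAP 5.7.3.2 and protocol 3.1.

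The cost is a few lines of SAP text and one derivation from pre-dose eDiary data already collected. The restricted analysis has a slightly smaller denominator (495 instead of 550 per arm at f = 10%). SAP section 7 describes supportive analyses as already conducted; if the data are already unblinded, label the restricted analysis supportive.

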¹ **Screening/Baseline Phase** will be 3 - 28 days. The **Baseline Visit** may be scheduled but should only occur *after* all screening procedures are complete, patient meets inclusion/exclusion criteria, and lab test results have been received by the site.

² Patients will use eDiary to answer questions about their migraine symptoms upon experiencing a moderate/severe migraine headache. The patient will administer pre-dispensed study drug if 1) the headache remains moderate or severe; 2) the patient has completed all required migraine assessment questions in the eDiary, including their current most bothersome migraine symptom, and 3) the patient has not already taken prohibited medications (see protocol section 5.4).

³ Patients should keep track of their concomitant medications throughout the study and report them to the study personnel at the End of Treatment Visit. Any medication taken for recurrent headache should be documented. Use of concomitant medications after randomization, including rescue medications, will be recorded by the patient on a paper diary and reported to the site.

⁴ Height will only be captured at the Screening Visit. Weight body temperature, respiratory rate, blood pressure and heart rate will be collected at all time points where indicated. Sitting arterial systolic and diastolic blood pressure and pulse rate will be measured.

⁵ All Screening Visit laboratory test results must be received prior to Baseline Visit.

⁶ A serum pregnancy test will be completed at Screening and End of Treatment Visits as part of the standard laboratory tests (if appropriate). Confirmatory urine pregnancy test for WOCBP should be completed on site at Baseline Visit and any subsequent visits for confirmation at the Investigator's discretion. Home pregnancy test will be provided to WOCBP after completion of baseline visit.

⁷ SAEs are reported from the time of informed consent and non-serious AEs are reported from baseline. All ongoing non-serious AEs and SAEs will be followed to resolution or until investigator deems there will be no further status change. SAE and AE's that occur during the treatment period should be reported to the site.

⁸ This scale will be clinician administered, completed on site, and will be in paper. The source document will be provided by Biohaven. The assessment period for completing the scale will be 30 days prior to Screening, and since the last visit for the remainder of the study.

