5.7.2 MBS Recored After IP is Taken

Subjects that record their MBS after taking the investigation product (IP) are considered failures for the analysis of MBS.

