3.2 Freedom from MBS at 3 Hours Post Dose

The estimand, difference in percentage of subjects with freedom from MBS at 3 hours between treatment groups was evaluated by computing the common risk difference using CMH weights (sample size weights), stratified by the use of prophylactic migraine medication (yes or no). The risk difference was tested at a two-sided alpha level of 0.05. Missing data at 3 hours post-dose was imputed as failure (NC=F). Also the use of rescue medication prior to providing data at the 3 hour assessment, taking IP prior to reporting the MBS, or failure to report a MBS are events that were imputed as treatment failures.

Results presented for this analysis included the following:

- Common risk difference with sample size, p-value, ASE, and 95% asymptotic CIs.
- Risk difference within each strata with sample size, p-value, ASE, and 95% asymptotic CIs.
- A plot of the risk differences within each strata, and common risk difference (similar to the risk difference plot produced by SAS Proc Freq).
- Common risk for each treatment with sample size, ASE, and 95% asymptotic CIs.

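### One sentence in SAP 5.7.3.2 reverses the MBS-timing failure rule for a co-primary endpoint, against every other statement of that rule

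*SAP*

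**What the plan says.** The derivation text in SAP 5.7.3.2 reads: "Subjects who reported their MBS before taking IP, or who did not provide an MBS are considered failures in this analysis".

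The other statements on the timing of the MBS report are:

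- SAP 5.7.3.2, imputation paragraph: "taking IP prior to reporting the MBS, or failure to report a MBS are events that are imputed as treatment failures".
- SAP 5.7.3.2, first tabulation bullet, which counts separately "subjects with a missing MBS, and subjects who reported their MBS after taking study medication".
- SAP 2.3.1, Table 1, intercurrent events for the MBS estimand: "Study medication taken before reporting MBS=F".
- SAP 5.7.2, a section given over to this rule: "Subjects that record their MBS after taking the investigation product (IP) are considered failures for the analysis of MBS".
- SAP Appendix 3, section 3.2, for the ad-hoc 3-hour MBS analysis: "taking IP prior to reporting the MBS, or failure to report a MBS are events that were imputed as treatment failures".
- Protocol 6.3.2: "The most bothersome symptom must be identified before the subject takes study medication".
- Protocol 4.3, Table 1, footnote 2, which allows dosing only once "the patient has completed all required migraine assessment questions in the eDiary, including their current most bothersome migraine symptom".

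Protocol 9.4.1, on the primary analysis, has no rule on MBS timing, so the SAP alone sets it.

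**The concern.** The first SAP sentence and the imputation paragraph of the same section cannot both be the intended derivation. One fails subjects who reported before dosing and the other fails subjects who reported after. The sentence as printed penalises those who followed the protocol.

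The location is what gives this weight. Freedom from MBS is one of two co-primary endpoints, and under SAP 5.2.5 both must be significant before any secondary endpoint is tested. The same derivation carries into the subgroup analyses and the sensitivity analyses of MBS, which repeat the primary analysis. A programmer or outside reader who took the sentence at face value would derive a different and meaningless endpoint.

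**Working it through.** **Comparison of the text.** An mITT subject reported the MBS before IP, reported it after IP, or did not report it.

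| Source | Before IP | After IP | No MBS |
|---|---|---|---|
| SAP 5.7.3.2, disputed sentence | failure | not mentioned | failure |
| SAP 5.7.3.2, imputation paragraph | not failed | failure | failure |
| SAP Table 1 | not failed | failure | failure |
| SAP 5.7.2 | not failed | failure | not mentioned |
| SAP Appendix 3, 3.2 (3 hours) | not failed | failure | failure |

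The disputed sentence differs only in the timing half. Its rule on a missing MBS agrees with Table 1 and the imputation paragraph. If the sentence and the imputation paragraph are both applied literally, all three groups fail and no mITT subject can succeed.

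**The plan's own figure.** SAP 5.1 states more than 95% power for MBS with 550 per group but gives no MBS response rates, so the figure cannot be reproduced exactly. With the Phase 2b single-symptom rates as proxies and no late reporters, power at 550 per arm is 99.98% for nausea and above 99.99% for photophobia and phonophobia. That is compatible with the stated figure.

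**Illustration of the two readings.** Inputs:

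- 2-hour freedom rates, 75 mg versus placebo (Protocol 1.4.2): photophobia 41.9% and 24.1%, phonophobia 52.3% and 28.1%, nausea 67.4% and 51.2%.
- n = 550 per arm, two-sided alpha 0.05.
- Assumed share L reporting the MBS after dosing: 1%, 5% or 10%, equal in both arms and unrelated to response.

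Formulas: under the intended rule (late report = failure) the success rate is (1 − L) × p. Under the disputed sentence alone, only late reporters can succeed, so the rate is L × p. The test is an unstratified Wald test of the risk difference (RD) with unpooled variance.

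Worked case, photophobia with L = 5%:

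- Intended rule: 0.95 × 41.9% = 39.8% and 0.95 × 24.1% = 22.9%, an RD of 16.9 points and power above 99.9%.
- Sentence alone: 0.05 × 41.9% = 2.095% and 0.05 × 24.1% = 1.205%, an RD of 0.89 points. Expected responders are 550 × 0.02095 = 11.5 and 550 × 0.01205 = 6.6, or about 12 and 7. SE = √[(0.02095 × 0.97905 + 0.01205 × 0.98795)/550] = 0.00768, so z = 0.0089/0.00768 = 1.16. Power ≈ Φ(1.16 − 1.96) = 21%.

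All cases, in the order L = 1% / 5% / 10%:

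| Proxy | Intended: RD (points) | Intended: power | Sentence alone: RD (points) | Sentence alone: power |
|---|---|---|---|---|
| Photophobia | 17.6 / 16.9 / 16.0 | >99.9% throughout | 0.18 / 0.89 / 1.78 | 6 / 21 / 38% |
| Phonophobia | 24.0 / 23.0 / 21.8 | >99.9% throughout | 0.24 / 1.21 / 2.42 | 8 / 30 / 54% |
| Nausea | 16.0 / 15.4 / 14.6 | 99.98 / 99.9 / 99.8% | 0.16 / 0.81 / 1.62 | 5 / 12 / 20% |

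The powers for the sentence alone come from simulation (400,000 replicates). Normal-approximation formulas give values within about one to two points. At L = 0 the sentence leaves no successes in either arm and no test is possible.

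**The case against.** The contradiction is not disputable; its weight is. The rule is given the other way round in the places that should control: the estimand table, a section devoted to it, and the paragraph of 5.7.3.2 that also sets the test and alpha. To code the sentence literally, a programmer would have to ignore all of these. Coding both rules together would fail everyone, which would be noticed at once. Appendix 3, written in the past tense, reports the 3-hour MBS analysis with the intended direction, which suggests the rule was understood in practice. On this view the point is an erratum, and the literal-reading powers lend it false weight: they rest on an assumed late-report rate and proxy response rates, and at L = 1% with photophobia rates about 2 responders against 1 is no basis for an asymptotic test.

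Most of this stands. Intent is recoverable, a silent error is unlikely, and the literal-reading figures are not a forecast. Two things limit it. Appendix 3 concerns a different, ad-hoc endpoint and does not show how the 2-hour endpoint was programmed. And the slip reverses a failure rule in the section that defines a co-primary endpoint, so it is more than cosmetic even when other sections allow it to be corrected.

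**Conclusion.** The point holds and should be fixed. As printed, the sentence is wrong: it fails the protocol-compliant subjects and contradicts the rest of the SAP. The conclusion rests on the text alone and on no numerical assumption.

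Under the rule stated everywhere else, the endpoint is computable and the sample size and power are unaffected, with proxy power at least 99.8% in all nine cases examined. The drop to about 5% to 54% belongs only to the literal reading of the sentence. It depends on the assumed late-report share, on its being equal across arms and unrelated to response, and on single-symptom Phase 2b rates standing in for MBS rates. The defect is an avoidable contradiction in a primary derivation, not a flaw in the design or the test.

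**What to change.** In the disputed sentence of SAP 5.7.3.2, replace 'before' with 'after', so that subjects who reported their MBS after taking IP, and those who reported none, are the failures. The sentence then agrees with Table 1, 5.7.2, the imputation paragraph of 5.7.3.2 and Appendix 3, section 3.2. The cost is one word. Data, sample size, test and testing order all stay as they are, and there is no downside.
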